5.6 VISIT 3 – WEEK 12 (END OF TREATMENT PHASE)

After 12 weeks of treatment, participants will be invited to return to hospital. This will mark the end of their treatment phase and they will return their allocated study device. Assessment and data collection will be collected as follows:

- Blood test (HbA1c only)
- Michigan Neuropathy Screening Instrument (MNSI)
- Nerve conduction study (NCS bilateral testing of sural, common peroneal, tibial and superficial peroneal nerves) (central site only)
- Quantitative Sensory Testing (QST) (central site only)
- Berg Balance Scale (BBS)
- Neuropathic Pain Symptom Inventory (NPSI)
- Total Symptom Score (TSS)
- Monofilament test
- Device sensory threshold and suprathreshold
- Device experience questionnaire A simple device use questionnaire will be taken to report ease of device use and suggest any developments
- Collection of patient diary
- AE (safety reporting) and concomitant medication check

5.7 VISIT 4 – WEEK 26 (FOLLOW UP)

At 26 weeks, participants will be invited to return to hospital. This will mark their final trial visit and completion of the study. Assessment and data collection will be collected as follows:

Michigan Neuropathy Screening Instrument (MNSI)

Research Governance and Integrity Team

- Nerve conduction study (bilateral testing of sural, common peroneal, tibial and superficial peroneal nerves) (central site only)
- Quantitative Sensory Testing (QST) (central site only)
- Mobility/Balance test (Berg Balance Scale)
- Neuropathic Pain Symptom Inventory (NPSI)
- Total Symptom Score (TSS)
- Monofilament test
- Device sensory threshold and suprathreshold
- AE (safety reporting) and concomitant medication check

5.8 INCIDENTAL FINDINGS

Incidental findings may potentially be identified during study assessments, such as blood and pregnancy tests. These will be reported to the GP with the consent of the patient.

.

6. RECORD KEEPING AND DATA PROTECTION 6.1 SOURCE DATA

Participants in the study will be identified using a unique study number, which will be used to label all documentation. A list of patient details will be kept in a locked filing cabinet at the local clinical trial site. Data will be written directly into the CRF and then transcribed into the eCRF (REDCap). The Medical Dictionary for Regulatory Activities (MedDRA) dictionary will be used as the coding system for the study. Source documents include original documents related to the trial, medical treatment and history of the participant, and adequate source documentation will be maintained to allow reliable verification and validation of the trial data.

6.2 LANGUAGE

CRFs will be in English. All written material to be used by participants will use vocabulary that is clearly understood and be in the language appropriate for the study site.

6.3 DATABASE

The principal means of data collection and storage will be the eCRF, provided by the internet-based REDCap database system. Data will be entered into the eCRF system by clinical trial site staff and will be viewable through data entry access. The type of activity site staff may undertake on the database will be regulated by authorisations set up by the Trial Manager/Monitor. Where applicable, the option to select a value from a list of valid options will be

Imperial College Healthcare

Research Governance and Integrity Team

available. Valid rules and range checks, for example, will be set up on the database to ensure data integrity and queries will be generated by programmes designed to detect missing or erroneous data. The Trial Monitor will also be able to create data queries on missing or erroneous data identified through remote monitoring or source data verification. Clinical trial site staff will need to respond to these queries in a timely manner to ensure data integrity. Any data changes will also need to be updated on the source documentation and signed and dated by the clinical trial site staff to provide a paper trail. Regular reports will be sent to sites from the Trial Monitor detailing outstanding queries. All source data recorded in the CRF and data recorded in the eCRF will be signed by the local PI or delegate. All changes made following the electronic signing will have an electronic audit trail with a signature and date.

It is the policy of Imperial College London to retain all trial data for 10 years after a study has ended. All data, whether held electronically or manually, will be kept securely, backed up regularly (if electronic) and not disclosed unlawfully. The data custodian is Imperial College London. Actegy Limited will process the Revitive App data on behalf of Imperial College London and are therefore a data processor for this study.

6.4 MONITORING

The study will be monitored periodically to assess the progress of the study, verify adherence to the protocol, GCP guidelines and other national/international requirements and to review the completeness, accuracy and consistency of the data. Monitoring will be undertaken by the Trial Monitor and self-compliance checklists will be performed by site staff. Monitoring procedures and requirements will be documented in a **Monitoring Plan**, developed in accordance with the risk assessment and will follow a risk-based approach when determining the level of onsite and remote monitoring.

7. ASSESSMENT OF SAFETY

7.1 DEFINITIONS

7.1.1 INVESTIGATIONAL MEDICAL DEVICE

The medical device being assessed for safety or performance in a clinical investigation. This includes medical devices already on the market that are being evaluated for new intended uses, new populations, new materials or design changes.

The medical device being investigated for this trial is the Revitive Medic Coach. The device is suitable for healthy individuals or people with poor circulation, a sedentary lifestyle, limited mobility, following surgery or injury

Imperial College Healthcare

Research Governance and Integrity Team

and those with diabetes (including DN), osteoarthritis, peripheral arterial disease, chronic venous insufficiency and chronic obstructive pulmonary disease. The device is safe to use in patients and there are very few clinical risks associated with the use of NMES devices. There is no expected risk in patients with DN, if the exclusion criteria are adhered to.

Further details on the NMES device can be found in in the **Instructions for Use (IFU)** and **Investigator's Brochure (IB)**.

7.1.2 ADVERSE EVENT (AE)

An Adverse Event (AE) is any untoward medical occurrence, unintended disease or injury, or any untoward clinical signs (including an abnormal laboratory finding) in participants, users or other persons concerned with the medical device. These may, or may not be, considered related to the investigational device, device related procedure or comparator. If the AE is considered to have a reasonable causal relationship with the device, then it is considered to be an Adverse Device Effect (ADE).

7.1.3 ADVERSE DEVICE EFFECT (ADE)

An Adverse Event (AE) related to the use of an investigational medical device. This includes any AE resulting from insufficiencies or inadequacies in the instructions for use, the deployment, implantation or operation of the medical device or any malfunction. This also includes any AE that is a result of an error in use or intentional misuse of the medical device.

7.1.4 DEVICE DEFICIENCY

Inadequacy of a medical device with respect to its identity, quality, durability, reliability, safety or performance. Device deficiencies include malfunctions, misuse or use errors and inadequate labelling.

7.1.5 SERIOUS ADVERSE EVENT (SAE)

An Adverse Event (AE) that results in:

- Death.
- Life threatening illness or injury.
- Permanent impairment of a body structure or body function.
- Hospitalisation or prolongation of existing hospitalisation.
- Medical or surgical intervention to prevent life threatening illness, injury or impairment to a body structure or body function.
- Foetal distress, foetal death or congenital anomaly or birth defect.
- Is otherwise considered medically significant by the Investigator.

Imperial College Healthcare

Research Governance and Integrity Team

This includes potential SAEs which were avoided as result of action or intervention. A planned hospitalisation for a pre-existing condition, or a procedure required in the protocol, without a serious deterioration in health, is not considered an SAE.

NOTE: Device deficiencies that might have led to a SAE where a suitable action had not been taken or an intervention had not been made or if circumstances had been less fortunate are handled under the serious adverse event reporting system.

Such AEs should be reported as soon as possible.

Medical judgement should be exercised in deciding whether an adverse event is serious in other situations. Important adverse events that are not immediately life-threatening or do not result in death or hospitalisation but may jeopardise the subject or may require intervention to prevent one of the other outcomes listed in the definition above, should also be considered serious.

Severity: The term "severe" is often used to describe the intensity (severity) of a specific event. This is not the same as "serious", which is based on patient/event outcome or action criteria.

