2. STUDY OBJECTIVES AND OUTCOME MEASURES

2.1 PRIMARY OBJECTIVES

The primary objectives are to assess the potential efficacy signal, feasibility and safety of a NMES device as an adjunct to standard of care in people with DN.

The potential efficacy signal of a NMES device as an adjunct to standard of care will be primarily assessed by a change in neuropathy symptoms from baseline to the end of the treatment phase (12 weeks), compared to a sham device as an adjunct to standard of care. Neuropathy symptoms will be measured using the MNSI and will also be evaluated at follow up 6 weeks and 26 weeks, but the end of the treatment phase (12 weeks) will be the primary timepoint of interest.

The feasibility of a NMES device as an adjunct to standard of care will be assessed through recruitment rate, which will compare number of patients pre-screened/identified and number of participants recruited at baseline, participant retention rate, which will compare number of participants randomised and number of participants on study at the end of the treatment phase (12 weeks) and follow up (26 weeks), and adherence to treatment at the end of the treatment phase (12 weeks), which will be measured through the Revitive App and a patient diary.

Imperial College Healthcare

Research Governance and Integrity Team

The safety of a NMES device as an adjunct to standard of care will be assessed through reporting of Adverse Events (AEs), Adverse Device Effects (ADEs), Serious Adverse Events (SAEs) and Serious Adverse Device Effects (SADEs). For further details of assessment of safety and definitions please see **7. ASSESSMENT OF SAFETY**.

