2.6 SAFETY OUTCOME MEASURES

- Adverse Events (AEs) collected and reported via AE form
- Adverse Device Effects (ADEs) collected and reported via AE form
- Serious Adverse Events (SAEs) collected and reported via SAE form
- Serious Adverse Device Effects (SADEs) collected and reported via SAE form

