7.1.6 SERIOUS ADVERSE DEVICE EFFECT (SADE)

An Adverse Device Effect (ADE) that results in:

- Death.
- Life threatening illness or injury.
- Hospitalisation, or prolongation of existing hospitalisation.
- Persistent or significant disability or incapacity.
- Foetal distress, foetal death or congenital anomaly or birth defect.
- Is otherwise considered medically significant by the Investigator.

But has previously been identified in the **Study Protocol** and/or **Investigator Brochure (IB)**.

Any hospitalisation planned prior to enrolment is not a SADE.

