7.4.6 PREGNANCY

Where relevant, any pregnancy occurring during the clinical study and the outcome of the pregnancy should be recorded on a Pregnancy Notification Form. Patients will be asked to consent to be followed up for congenital abnormality or birth defect. Pregnancy is considered an SAE, the patient will be asked to stop using the device, followed up according to the protocol and the results analysed as per intention to treat.

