8.2.3 SAFETY OUTCOME MEASURES ANALYSIS

All safety variables will be summarised by treatment in the form of frequency tables for categorical variables or descriptive statistics for continuous variables. The MedDRA dictionary will be used as the coding system for the study. An AE will be considered treatment emergent if it started after the first use of the device (NMES or sham device). Adverse events will be categorised by MedDRA System Organ Class and Preferred Term. Treatment emergent AEs will also be summarised (incidence and frequency) by severity and relationship to treatment.

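### The SAE and SADE outcomes rest on inconsistent seriousness definitions, so serious-event counts by arm can be misclassified.

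*Protocol*

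**What the plan says.** Section 2.6 names both outcomes: "Serious Adverse Events (SAEs) collected and reported via SAE form" and "Serious Adverse Device Effects (SADEs) collected and reported via SAE form". Section 2.1 makes safety one of the primary objectives and points to section 7: "For further details of assessment of safety and definitions please see". Section 8.2.3 states: "All safety variables will be summarised by treatment in the form of frequency tables". The definitions in section 7 therefore decide what enters those tables.

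Section 7.1.5 defines an SAE as an adverse event that results in one of seven outcomes, the last being the investigator's judgement of medical significance. It then adds: "This includes potential SAEs which were avoided as result of action or intervention". Section 7.4.6 adds, with no condition on how the pregnancy goes: "Pregnancy is considered an SAE". Section 7.1.6 gives a separate list of six outcomes for SADEs, one of which is "Persistent or significant disability or incapacity".

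**The concern.** A SADE should be an SAE that is related to the device. That requires both definitions to use the same test of seriousness, and here they do not. In addition, the SAE definition takes in occurrences in which no listed outcome need have arisen: avoided events and uncomplicated pregnancies. Both are worth reporting. Counted together with events that happened, however, they make the SAE figure hard to interpret.

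Section 1.1.5 makes a judgement that the device is safe one of the conditions for a larger trial, and section 9.8 says no data monitoring committee will be convened. The small serious-event tables from this pilot will carry much of that judgement, so it should be clear what they count.

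**Working it through.** **Step 1. The two lists side by side** (criteria paraphrased).

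| Criterion | SAE (7.1.5) | SADE (7.1.6) |
|---|---|---|
| Death | yes | yes |
| Threat to life | yes | yes |
| Admission or a longer stay | yes | yes |
| Harm to the foetus or congenital abnormality | yes | yes |
| Investigator judges it medically significant | yes | yes |
| Bodily impairment, if permanent | yes | no |
| Treatment given to prevent a grave outcome | yes | no |
| Disability or incapacity that persists or is significant | no | yes |

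The SAE list has 7 items, the SADE list has 6, and 5 are shared. Two appear only under SAE and one only under SADE.

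**Step 2. What the mismatch does.**
- A device injury treated without admission, to prevent impairment, meets a named SAE criterion. It meets no named SADE criterion and becomes a SADE only if the investigator calls it medically significant.
- A device effect causing significant but not permanent disability meets a named SADE criterion. It meets no named SAE criterion and becomes an SAE only through the same judgement.

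The mismatch runs both ways, so on named criteria SADE is not a subset of SAE.

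**Step 3. Avoided events.** The opening words of 7.1.5 require that an outcome resulted, whereas the added sentence covers outcomes that did not. It can be read in two ways. If it means an adverse event that occurred and was treated before it worsened, it largely repeats the treatment-to-prevent criterion. If it means that nothing serious happened, it counts non-events. The protocol does not say which is meant. Section 7.4.3 shows that a separation is possible: it lists device deficiencies with SAE potential as an item apart from SAEs.

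**Step 4. Pregnancy.** The only pregnancy-related items in 7.1.5 concern foetal harm and congenital abnormality. An uncomplicated pregnancy meets neither, so 7.4.6 adds it by declaration.

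**Step 5. Size.** The protocol states no expected SAE, SADE or pregnancy rate, so there is no figure of its own to reproduce. Inputs: 32 participants per arm (section 8.1), and safety analysed in all randomised participants (section 8.2). Shift in an arm's rate for k misclassified participants = 100 × k / 32:
- k = 1: 3.1 percentage points
- k = 2: 6.25 percentage points
- k = 3: 9.4 percentage points

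As an illustration only, one SADE missed in an arm changes 1/32 (3.1%, exact 95% CI 0.1% to 16.2%) to 0/32 (0%, exact 95% CI 0% to 10.9%).

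**The case against.** A reader might infer that the two tables will be wrong in opposite directions, with SAEs overcounted and SADEs undercounted. The documents do not support that, for these reasons:

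- Both lists end with the same investigator catch-all. Section 7.1.5 also tells investigators to treat as serious an important event that may need intervention to prevent a listed outcome. An adverse device effect is by definition an adverse event, so this guidance reaches device-related events too. Omitted SADEs can be recovered.
- The disability wording in 7.1.6 is not limited to permanent harm, so on that item SADE may be the broader definition.
- Section 7.1.5 says only that near-miss device deficiencies are handled through the SAE reporting system, and 7.4.3 lists them separately. They are not plainly SAEs.
- Pregnancies should be few. Section 4.3 excludes pregnant patients and section 5.4 requires non-childbearing potential, or contraception with a negative test. Those that occur go on their own notification form and can be identified.
- The definitions are the same in both arms and assessors are blinded. Nothing shows that avoided events would be more frequent with the active device.
- Table layout belongs to the SAP, which is not shown, and its absence from the protocol is no fault.

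All of this stands, and it limits the claim to a risk of misclassification of unknown direction. It does not remove the inconsistency. Whether an event enters the SADE count should not depend on a catch-all when the parallel SAE definition names the criterion. The definitions themselves are fixed in the protocol and are not left to the SAP.

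**Conclusion.** The inconsistency is real and should be corrected. Sections 7.1.5, 7.1.6 and 7.4.6 do not apply one test of seriousness, and SAE and SADE counts by arm can be misclassified as a result. Each misclassified participant is worth 3.1 percentage points in an arm of 32, assuming the target size is reached and all randomised participants form the denominator. How many would be affected cannot be computed, because the protocol gives no event rates. The net direction is not known, no bias between arms is shown, and section 1.1.5 sets no numerical safety threshold that one event would cross.

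A separate matter is that 7.1.6 limits SADEs to effects already identified, while 7.1.7 defines the unanticipated kind as a SADE that has not been identified. This point does not rest on that conflict, but a common list will not resolve it.

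**What to change.** 1. **Sections 7.1.5 and 7.1.6:** use one seriousness list containing the criteria of both, including treatment given to prevent harm and persistent or significant disability. Define a SADE as an adverse device effect that meets any item on it. Simply pointing 7.1.6 to the present 7.1.5 list would lose the disability item. For SADE to be the full device-related subset of SAE, the previously-identified condition in 7.1.6 must also be reconciled with 7.1.7.
2. **Section 8.2.3 (or the SAP):** count as SAEs in the tables by arm only events that occurred and met a criterion. An adverse event that was treated to prevent a grave outcome stays in the count under that criterion. List separately by arm the avoided events that met no criterion, near-miss device deficiencies, and pregnancies without an untoward outcome.
3. **Section 7.4:** leave reporting to the MHRA and the sponsor unchanged. Pregnancy can remain reportable in the way 7.4.6 requires.

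The cost is a few sentences of wording and no new data collection. Because recruitment began in August 2023 (section 3.5), adverse-event and SAE records already completed should be checked once against the common list, blind to allocation and before database lock.

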7.1.6 SERIOUS ADVERSE DEVICE EFFECT (SADE)

An Adverse Device Effect (ADE) that results in:

- Death.
- Life threatening illness or injury.
- Hospitalisation, or prolongation of existing hospitalisation.
- Persistent or significant disability or incapacity.
- Foetal distress, foetal death or congenital anomaly or birth defect.
- Is otherwise considered medically significant by the Investigator.

But has previously been identified in the **Study Protocol** and/or **Investigator Brochure (IB)**.

Any hospitalisation planned prior to enrolment is not a SADE.

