7.1.7 UNANTICIPATED SERIOUS ADVERSE DEVICE EFFECT (USADE)

Serious adverse device effect (SADE) which by its nature, incidence, severity or outcome has not been identified in the current version of the risk analysis report.

Imperial College Healthcare

Research Governance and Integrity Team

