7.3.2 ASSESSMENT OF EXPECTEDNESS

Anticipated: The reaction is consistent with the effects of the device listed in the **Investigator Brochure (IB)** or **Study Protocol**.

Unanticipated: the reaction is not consistent with the effects of the device listed in the **Investigator Brochure (IB)** or **Study Protocol**.

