7.4.4 USADEs

If an SAE is determined to be unanticipated (not previously described in the **Investigator Brochure (IB)** or **Study Protocol**) and related to the study device then it is considered an USADE. For USADEs, in addition to reporting to the MHRA as described in the sections above, the CI must also report the event to the REC in the UK and make sure the event is reported to Ethics Committees in participating countries as required. Reports should be made to the REC within **15 days** according to HRA website using the non-CTIMP SAE form. The Device Manufacturer and Investigators at all sites should be notified of the USADE.

Unblinding might have to be considered in the event of a USADE, although unblinding should be avoided where possible.

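### Section 7.1.6 limits a SADE to effects already identified in the protocol or Investigator Brochure, so read literally the SADE outcome omits unanticipated serious device effects; 7.1.7 and 7.4.4 then judge unanticipated against different documents

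*Protocol*

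**What the plan says.** All references are to the Protocol.

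- **Objective and outcomes.** Section 2.1 opens: "The primary objectives are to assess the potential efficacy signal, feasibility and safety of a NMES device". Sections 2.1 and 2.6 and Table 1 name four safety outcomes: AEs, ADEs, SAEs and SADEs. USADEs are not a named outcome.
- **SADE (7.1.6).** An ADE that meets one of a list of seriousness criteria, followed by the condition "But has previously been identified in the" Study Protocol and/or IB.
- **USADE (7.1.7).** A SADE "which by its nature, incidence, severity or outcome has not been identified in the current version of the risk analysis report".
- **USADE (7.4.4).** "If an SAE is determined to be unanticipated (not previously described in the" IB or Study Protocol) and is related to the device, it is a USADE.
- **Expectedness (7.3.2).** A reaction is unanticipated when "the reaction is not consistent with the effects of the device listed in the" IB or Study Protocol.
- **Consequence of the label.** Section 7.2.1 restricts ethics committee (REC) reporting to USADEs. Section 7.4.4 attaches a 15-day REC report, notice to the manufacturer and to investigators at all sites, and possible consideration of unblinding.

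**The concern.** In ordinary use, a SADE is any serious event caused by the device, and anticipated and unanticipated effects are its two subdivisions. Section 7.1.6 instead makes being anticipated a condition of being a SADE at all. A SADE table built to that definition would leave out the serious device effects that nobody foresaw, which are those of most interest in a pilot with a safety objective. No other named outcome isolates events that are both serious and device-related.

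The second problem concerns the label. Whether an event is a USADE decides whether it goes to the REC, and the protocol gives two tests that refer to different documents. Two people classifying the same event in good faith could reach different answers.

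**Working it through.** The protocol gives no figure to reproduce here. The check is whether the definitions agree when applied to the same event.

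**Inputs.** Take any serious, device-related event and ask two questions: is it in the protocol and/or IB (the test in 7.1.6, 7.3.2 and 7.4.4), and is it in the risk analysis report (the test in 7.1.7)?

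**Step 1: the text as it stands.** Section 7.1.7 builds on SADE, so it carries the 7.1.6 condition with it.

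| In protocol and/or IB | In risk analysis report | SADE (7.1.6) | USADE (7.1.7) | USADE (7.4.4) |
|---|---|---|---|---|
| yes | yes | yes | no | no |
| yes | no | yes | yes | no |
| no | yes | no | no | yes |
| no | no | no | no | yes |

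The last two rows are the undercount: serious, device-related and unanticipated under 7.4.4, yet not SADEs. The last row also shows the contradiction. An event in none of the documents is the clearest USADE there could be, but it fails 7.1.7 because it is not a SADE.

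If protocol and IB are counted separately, there are 2 × 2 × 2 = 8 combinations. SADE covers 6 of the 8, USADE by 7.1.7 covers 3, and USADE by 7.4.4 covers 2.

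**Step 2: the text with the 7.1.6 condition removed.**

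| In protocol and/or IB | In risk analysis report | SADE | USADE (7.1.7) | USADE (7.4.4) |
|---|---|---|---|---|
| yes | yes | yes | no | no |
| yes | no | yes | yes | no |
| no | yes | yes | no | yes |
| no | no | yes | yes | yes |

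SADE now covers everything it should. The two USADE tests agree in the first and last rows and disagree in the middle two. Of the 8 combinations, 7.1.7 covers 4, 7.4.4 covers 2, and 1 is shared. That leaves (4 − 1) + (2 − 1) = 4 in disagreement. Removing the clause therefore repairs the SADE outcome but not the USADE label, because the reference documents still differ.

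**Step 3: which reading was intended.** Three features suggest that the 7.1.6 clause is misplaced. Section 7.1.7 treats a USADE as a type of SADE. Section 7.4.2, which covers SAEs and SADEs together, has expectedness recorded; that would be redundant for SADEs if all of them were anticipated. The glossary lists an anticipated category (ASADE) that 7.1 never defines, and the clause reads like its definition.

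**Step 4: size.** These are combinations of definitions, not probabilities. The protocol states no expected SADE rate, and 1.1.3 refers the risks to the IFU and IB, which are not at hand. As a scale only: with 32 per group (8.1), one participant whose only serious device effect was unanticipated would move that arm's SADE proportion by 1/32 = 3.1 percentage points. With no such event, nothing changes.

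**The case against.** The strongest reply is that this is a drafting slip whose intent is recoverable, and that the working rules do not depend on it. Much of that stands. The SAE form records seriousness, causality and expectedness (7.4.2). Every SAE goes to the MHRA whether related or not (7.4.3). Section 7.4.4 builds its REC trigger from SAE, relatedness and absence from the IB or protocol, without using the term SADE. Section 7.2.2 lists SAE reporting to the REC and MHRA more broadly still. The safety analysis in 8.2.3 specifies no SADE proportion or interval. Sites working from 7.4 could classify and count correctly. What does not stand is that the slip is harmless: 7.1.6 is the operative definition of a named outcome, and applied as written it gives the wrong class.

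Three stronger readings are tempting, and the documents do not support them.

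- **That the two USADE definitions are mutually exclusive.** Step 1 shows no overlap, but only because 7.1.7 inherits the stray clause. It also requires treating identified and described as the same test, and taking 7.4.4 to mean absent from both IB and protocol. If absence from either one is enough, 2 of the 8 combinations overlap; without the clause, the definitions overlap anyway. The supportable statement is that they use different reference documents.
- **That 7.3.2 adds a third test.** Its wording is looser, but it refers to the same documents as 7.4.4.
- **That the differing seriousness lists lose events.** "Permanent impairment of a body structure or body function" and "Medical or surgical intervention to prevent life threatening illness, injury or impairment to a body structure or body function" appear only in 7.1.5, and "Persistent or significant disability or incapacity" only in 7.1.6. Both lists include a medically significant item, and an ADE is an AE (7.1.3), so 7.1.5 already applies to it. No lost event can be shown.

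**Conclusion.** The point holds in two parts. First, read literally, 7.1.6 removes unanticipated serious device effects from the SADE outcome and contradicts 7.1.7. Second, 7.1.7 on one side and 7.3.2 with 7.4.4 on the other judge unanticipated against different documents, so an event listed in one source but not the other is classified differently.

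A reader might infer that safety events would go missing or unreported; the documents do not support that. A serious effect in neither the IB nor the protocol is still an ADE and an SAE, still goes to the MHRA, and still reaches the REC if 7.4.4 is followed. The main REC uncertainty is an event in the IB or protocol but not in the risk analysis report. Whether such an event exists depends on documents not at hand.

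The harm is therefore a possible undercount of one named outcome and an unclear label. It is conditional on an unanticipated serious device effect occurring and 7.1.6 being applied as written. It should be corrected, but it does not threaten the trial's safety data.

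**What to change.** 1. **Section 7.1.6.** Remove the closing condition, or move it to a separate definition of the anticipated category (ASADE) in 7.1. Either way, SADE should cover anticipated and unanticipated effects.
2. **Sections 7.1.7, 7.3.2 and 7.4.4.** Reconcile these to one named reference document for unanticipated. Edit 1 alone leaves 4 of the 8 combinations in disagreement, so both edits are needed.

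The cost is a protocol amendment while the trial is under way, handled under 9.2, and relabelling of any affected events. No new data are needed, because seriousness, causality and expectedness are already on the SAE form (7.4.2).
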